#### 6.4. Baseline Physical Exam

A standard physical exam will be performed during the Screening Period. Baseline findings will be recorded on the eCRF.

#### 6.5. Clinical Laboratory Tests

A negative serum pregnancy test must be confirmed at Screening for all females of childbearing potential. A blood sample for serum pregnancy testing will be taken from all females of childbearing potential at Screening. If the serum pregnancy test is positive, the patient must be discontinued from study treatment, unless subject is post-partum.

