### 4.3. Exclusion Criteria

Subjects will not be eligible for participation in the study if they meet ANY of the following criteria:

1. Baseline blood oxygen saturation ( $\text{SpO}_2$ )  $< 90\%$  at rest (refer to [Section 6.3.2](#)). For patients requiring routine supplemental oxygen,  $\text{SpO}_2$  measurements should be taken with the patient's normal oxygen supplementation.

2. Female subjects of childbearing potential with a positive serum pregnancy test at screening, or who are not taking (or not willing to take) acceptable birth control measures through the Follow-up Period. Adequate birth control methods include with a monogamous partner who was sterilized more than 6 months prior to screening, or measures with a Pearl index of  $<1$  used consistently and correctly (including intrauterine devices, or implantable, injectable, oral, or transdermal contraceptives). Women are not considered to be of childbearing potential if they meet at least 1 of the following 2 criteria as documented by the Investigator:
  - They have had a hysterectomy, bilateral salpingectomy, or bilateral oophorectomy at a minimum of 1 menstrual cycle prior to signing the ICF; or
  - They are post-menopausal: for women  $\geq 55$  years of age, defined as  $\geq 1$  year since their last menstrual period, or for women  $< 55$  years of age, defined as  $\geq 1$  year since their last menstrual period and have a follicle-stimulating hormone (FSH) level in the laboratory's normal range for post-menopausal phase.
3. Women who are lactating and insist on breast feeding.
4. Subjects who have received any other investigational therapy within 4 weeks prior to Screening.
5. Subjects who require anesthesia or heavy sedation to undergo MRI testing. Mild sedation could be acceptable (i.e. a low dose oral acting anxiolytic medication such as alprazolam) as long as, in the opinion of the investigator, the subject meets Inclusion Criteria #4 and #5.

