### 5.4. Method of Assigning Subjects to Treatment Groups

All randomized subjects will be divided between 2 treatment orders in a 1:1 ratio. Subjects will be randomized to receive either  $^{129}\text{Xe}$  followed by  $^{133}\text{Xe}$ , or  $^{133}\text{Xe}$  followed by  $^{129}\text{Xe}$ . All subjects will receive at least 1 dose of hyperpolarized  $^{129}\text{Xe}$  and 1 dose of  $^{133}\text{Xe}$  during study participation.

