## 6.2. Demographics, Medical History, and Concomitant Medications

Demographic information (age, race, gender, weight, height, smoking history, etc.) will be collected during the Screening Period. Medical history, including significant medical conditions, pulmonary function values, and surgical history, will also be collected during the Screening Period. Additionally, any medications taken as well as baseline signs and symptoms occurring within 2 weeks of screening will be recorded.

On the day(s) of the Imaging Period, any changes to the subject's condition that affect inclusion/exclusion criteria will be documented, as well as any additional medications taken. Subject must meet all inclusion/exclusion criteria upon entering the Imaging Period.

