 SpO2 is measured at baseline as well as before and after each scanning session (both Xe and Xe). An absolute decrease of SpO2 by greater than 10% is considered significant. If the subject is to receive another dose, the next dose will not be administered until the SpO2 is within 10% of its baseline value. If the subject has received their last dose, they will be observed until the SpO2 is within 10% of its baseline value. The subject will be monitored for the duration of the MRI exam by a qualified medical professional.

 Subjects will be monitored for any subjective sensation of residual anesthesia (e.g., lightheadedness, loss of sensation or awareness, loss of memory, or unconsciousness). If the subject is to receive another dose, the next dose will not be administered until the sensation has resolved. If the subject has received their last dose, they will be observed until the

sensation has resolved. The subject will be monitored for the duration of the MRI exam by a qualified medical professional.

 Eligibility assessment will include, if applicable, a negative pregnancy test.

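### Protocol 6.5 exempts post-partum women from the consequence of a positive pregnancy test, against Exclusion 2 and its own first sentence

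*Protocol*

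**What the plan says.** Section 6.5 (Clinical Laboratory Tests) has three sentences. The first sets the requirement: "A negative serum pregnancy test must be confirmed at Screening for all females of childbearing potential". The second says who is sampled: "A blood sample for serum pregnancy testing will be taken from all females of childbearing potential at Screening". The third gives the consequence of a positive result and carries the exception: "If the serum pregnancy test is positive, the patient must be discontinued from study treatment, unless subject is post-partum".

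Exclusion 2 in section 4.3, repeated in the synopsis, lists among those who may not take part: "Female subjects of childbearing potential with a positive serum pregnancy test at screening". It then defines the term: "Women are not considered to be of childbearing potential if they meet at least 1 of the following 2 criteria". The two criteria are specified surgery (hysterectomy, bilateral salpingectomy or bilateral oophorectomy) and post-menopausal status. Meeting any single exclusion criterion makes a subject ineligible.

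Two other places bear on the point. Section 6.2 says: "Subject must meet all inclusion/exclusion criteria upon entering the Imaging Period". Footnote 9 of the schedule in Protocol Appendix 1, reproduced in SAP Appendix 11.1, says: "Eligibility assessment will include, if applicable, a negative pregnancy test".

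**The concern.** Within one short section a site is told that every woman of childbearing potential needs a negative test, and then that a positive test need not stop a post-partum woman. The eligibility criteria contain no such allowance. Post-partum is not defined by a time since delivery, and the sentence asks for no repeat or confirmatory test. No section is stated to take precedence.

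What is at stake is subject protection. A coordinator working from the laboratory section could take the exception as the operative rule and let a test-positive woman go forward. She would then be exposed to both agents, because section 5.4 states "All subjects will receive at least 1 dose of hyperpolarized" 129Xe and one dose of 133Xe. There is also a small record-keeping consequence: her enrolment would breach 4.3 while complying with the last sentence of 6.5, so her classification under SAP 4.2.3 (Protocol Deviations) would be open to argument.

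**Working it through.** No arithmetic applies to the conflict itself. The check is to trace one case through each rule and then look for a reading that reconciles them.

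**Case:** a post-partum woman with a positive serum test at Screening, who has had none of the listed operations and is not post-menopausal.

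| Rule | Result for this woman |
|---|---|
| Exclusion 2 (4.3 and synopsis) | Ineligible; no exception |
| 6.5, first sentence | Requirement not met; no exception |
| 6.2 | May not enter the Imaging Period, because she meets Exclusion 2 |
| Footnote 9 | Negative test missing, if the footnote applies to her |
| 6.5, last sentence | Discontinuation not required |

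The first two rows conflict directly with the last. Section 6.2 is not a separate conflict, because it only enforces Exclusion 2. Footnote 9 supports the first two rows, but its qualifier about applicability leaves some room. The synopsis and SAP copies repeat rules and add none.

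**Could the exception have a valid use?** Four readings were tried.

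1. *Post-partum women are outside childbearing potential.* They are not. The definition gives two routes out, and having recently delivered is neither.
2. *The exception covers post-partum women who do meet one of those routes.* Such women are not of childbearing potential, so 6.5 does not sample them and there is no protocol test result for the sentence to act on.
3. *The sentence concerns a later test, after dosing has begun.* The schedule places the serum pregnancy test at Screening only, before any dose. For the same reason, discontinuing from study treatment is an odd description of what is in fact a failure to qualify.
4. *Exclusion 3 already removes post-partum women, so the clause is empty.* Exclusion 3 bars only lactating women who insist on breast feeding. Other post-partum women remain.

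The clause therefore reaches only women whom Exclusion 2 has already excluded.

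**Number affected.** The documents give none. As an illustration only, one such woman among the 32 planned completers would be 1/32 = 3.1%, and none is quite possible. She would have to be a lung-resection candidate, of childbearing potential, post-partum and test-positive within the Day -7 to Day 0 screening window.

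**The case against.** The strongest reply is that the clause does nothing. It governs discontinuation; it does not waive an exclusion criterion or authorise dosing. A site can obey every sentence of the protocol at once by excluding the woman. To dose her it would have to breach Exclusion 2, the first sentence of 6.5 and section 6.2. On this view the clause is stray wording, perhaps meant to allow for hormone that persists after delivery.

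Most of that stands. Read as a whole, the protocol should keep her out, and a reader who infers that it permits dosing of test-positive women goes further than the text. What survives is that the clause has no valid use, is harmless only when ignored, and sits in the section a site would consult when a result comes back. If residual post-partum positivity was the intent, the protocol does not say so.

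A reader might also count footnote 9 and the repeated copies as further contradictions. They are not: there are two direct conflicts, and the rest is support or repetition.

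A reader might also infer a documented fetal hazard. The documents do not give one. Section 1.4 reports that the cited reproductive and developmental literature shows no specific toxic effect of inhaled xenon. For 133Xe, the protocol calls the procedure nuclear scintigraphy and contrasts it with a non-radioactive product, but says nothing about risk in pregnancy. It refers dosing and administration to the Package Insert, which is not among the documents.

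**Conclusion.** The point holds as a minor subject-protection inconsistency. The last sentence of 6.5 conflicts directly with Exclusion 2 and with the first sentence of the same section, and no reading gives its exception a legitimate use. Exclusion 2, enforced by 6.2, should already prevent harm. The residual risk is that a site follows the exception and gives a test-positive post-partum woman both gases.

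Two assumptions lie behind treating this as worth correcting: that a site might act on 6.5 in isolation, and that exposure to 133Xe in a possibly pregnant woman is undesirable. The documents establish neither. The efficacy analysis, the target of 32 completers, the equivalence margins and the analysis-set definitions are unaffected.

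**What to change.** In 6.5, delete the closing exception for post-partum subjects. Replace the instruction to discontinue from study treatment with a statement that a woman of childbearing potential who tests positive at Screening is not eligible and is recorded as a screen failure. The section then agrees with Exclusion 2, and footnote 9 needs no change.

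If the sponsor did intend to allow for residual post-partum positivity, the alternative is a bounded exception written in the same terms into Exclusion 2 (synopsis and 4.3) and 6.5. It should give a maximum time since delivery and a confirmatory step that rules out a new pregnancy before either gas is given. Footnote 9 should then be aligned.

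The deletion costs one sentence in an amendment. It adds no test or visit, and it excludes no one whom Exclusion 2 does not already exclude. The bounded exception costs more, because it changes eligibility and adds a confirmatory step. If enrolment has already closed, which the documents do not state, the useful action is to check that no one was dosed on the strength of the exception.

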#### 6.6. MRI-suitable Screening

As indicated in exclusion criteria #5 ([Section 4.3](#)), a subject who requires anesthesia or heavy sedation in order to undergo MRI testing cannot participate in this study. However, mild sedation (i.e. a low dose oral acting anxiolytic medication such as alprazolam) could be acceptable if, in the investigator's opinion, the subject is still able to comply with all study procedures.

There are no additional protocol specific requirements or restrictions with respect to a subject being suitable for MRI testing.

#### 6.7. Spirometry Evaluation of FEV1

Pulmonary function will be evaluated by measuring FEV1 using spirometry prior to imaging on Day 1 (Imaging Period). For the sub-set of subjects undergoing surgery, FEV1 will also be measured during the Post-op Follow-up Period.

#### 6.8. Image Interpretation

As indicated in [Section 5.5](#), image interpretation will be performed by central readers. Details for performing image evaluation are provided in the [Imaging Manual](#).

## 6.9. Dispensing Study Drug

### 6.9.1. Study Drug – Hyperpolarized $^{129}\text{Xe}$ Gas Administration

The hyperpolarized  $^{129}\text{Xe}$  gas will be prepared by a technician using the BRANDNAME device located in a separate area (or room) close to the MRI suite. The device is comprised of 3 different components that hyperpolarize, measure the hyperpolarization of the  $^{129}\text{Xe}$  gas, and administer it to the patient (Figure 2). The technicians will be trained on the use of each of the device components prior to study initiation. In addition, the Operator's Manuals will be available during study execution.

**Figure 2 Depiction of the Hyperpolarization Process and Device Components**

The system functions by attaching a gas cylinder containing the Xe/He/N2 gas blend to the Hyperpolarizer. This system hyperpolarizes high purity, inert,  $^{129}\text{Xe}$  gas, which is collected as a solid in a cryogenic trap (a cold finger), then thawed, and dispensed into a 1 L delivery bag.

After dispensing an appropriate volume of Xe into the bag (based on dose required, e.g., full or calibration dose), the remaining bag volume is filled with ultra-high purity N2 buffer gas. Afterwards, the degree of  $^{129}\text{Xe}$  hyperpolarization is measured with the Polarization Measurement Station. The gas sample can be temporarily stored on the Polarization Measurement Station platform until it is needed for patient administration. To ensure that each

dose has sufficient polarization, the polarization will be measured within 5 minutes prior to administration to ensure the value is  $>10\%$ .

Additional information for preparation and administration of hyperpolarized  $^{129}\text{Xe}$  gas are provided in [Section 5.2.1](#) as well as the [IMP Handling and Labeling Instruction Manual](#) for this study.

#### 6.9.2. Anatomical Proton MRI (MRI Session Only)

During the MRI session, one or more conventional proton MRI scans will be collected to confirm lung anatomical features. Subjects will be required to take a full inhalation breath of room air and hold their breath for a maximum of 15 seconds while the MRI is acquired.

#### 6.9.3. Active Comparator – $^{133}\text{Xe}$ Administration

The active comparator,  $^{133}\text{Xe}$ , will be administered in accordance with the Package Insert. Detailed information for preparation and administration of  $^{133}\text{Xe}$  gas are provided in the [IMP Handling and Labeling Instruction Manual](#) for this study.

#### 6.10. Adverse Events Assessments

AEs will be reported using the current version of the Medical Dictionary for Regulatory Activities (MedDRA).

The investigator (and any sub-investigators) is responsible for the appropriate medical care of subjects during the study. The investigator remains responsible for following, through an appropriate health care option, serious adverse events (SAEs) or AEs that caused the subject to discontinue before completing the study. The subject should be followed until the event is resolved or explained. Frequency of follow-up evaluation is left to the discretion of the investigator.

##### 6.10.1. Adverse Events

An AE is any untoward medical occurrence in a subject participating in a clinical investigation/study that has received treatment with a drug or biologic (medicinal) product. The event does not necessarily have a causal relationship with the administration of the study drug. An AE can therefore be any unfavorable and unintended sign, symptom, or disease temporally associated with the use of a study drug, whether or not considered related to the study drug. This includes any side effect, injury, toxicity, or sensitivity reaction, and may include a single symptom or sign, a set of related symptoms or signs, or a disease. An AE may also be any laboratory abnormality judged to be clinically significant by the Investigator (or sub-investigator) that worsened when compared to baseline.

An abnormal laboratory value is not an AE unless it is considered to be clinically significant. AEs include the following:

- All suspected adverse drug reactions.
- All reactions from medication overdose, abuse, withdrawal, sensitivity, or toxicity.
- Apparently unrelated illnesses, including the worsening of a pre-existing illness.
- Injury or accidents. Note that if a medical condition is known to have caused the injury or accident (e.g., a fall secondary to dizziness), the medical condition (dizziness) and the accident (fall) should be reported as 2 separate AEs.
- Abnormalities in physiological testing or physical examination (findings that require clinical intervention or further investigation beyond ordering a repeat [confirmatory] test).
- Laboratory abnormalities that are clinically significant and require clinical intervention or further investigation (beyond ordering a repeat [confirmatory] test) unless they are associated with an already reported clinical event.

An AE **does not** include:

- Medical or surgical procedures (e.g., surgery, endoscopy, tooth extraction, transfusion); the condition that leads to the procedure is an AE.
- Pre-existing diseases or conditions present or detected at screening/baseline that do not worsen in severity or frequency.
- Situations where an untoward medical occurrence has not occurred (e.g., hospitalization for elective surgery, social and/or convenience admissions).
- Overdose of either study drug or concomitant medication without any signs or symptoms.

Throughout the course of the study, every effort should be made to remain alert to possible AEs. Subjects should be encouraged to report AEs spontaneously or in response to general, non-directed questioning.

With the occurrence of an AE, the primary concern is the safety of the subject. If necessary, appropriate medical intervention should be provided, and the study drug discontinued. Urgent safety issues may be discussed with physicians at the Contract Research Organization (CRO).

#### 6.10.1.1. Adverse Events of Special Interest

Subjective sensation of residual anesthesia (e.g., lightheadedness, loss of sensation or awareness, loss of memory, or unconsciousness) is an AE of special interest for this study. The next dose of any study treatment will not be administered until any sensation of residual analgesia has resolved. If the subject has received their last dose, they will be observed until the sensation of residual analgesia has resolved.

#### 6.10.1.2. Serious Adverse Events

An SAE is defined by federal regulation as any AE occurring at any dose that results in any of the following outcomes:

- Death.
- A life-threatening AE (i.e., immediate risk of death)  
**Note:** The term “life-threatening” in the definition of “serious” refers to an event in which the subject was at risk of death at the time of the event; it does not refer to an event which, hypothetically, might have caused death if it were more severe.
- Prolongation of existing hospitalization or re-hospitalization.
- Results in persistent or significant disability/incapacity.
- Is a congenital anomaly/birth defect.

Important medical events that may not result in death, be life threatening, or require hospitalization may be considered an SAE when, based upon appropriate medical judgment, the AE may jeopardize the subject and may require medical or surgical intervention to prevent one of the outcomes listed in this definition. Examples of such medical events include allergic bronchospasm requiring intensive treatment in an emergency room or at home; blood dyscrasias or convulsions that do not result in inpatient hospitalization, or the development of drug dependency or drug abuse.

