#### 6.10.3. Recording Adverse Events

When an AE/SAE occurs, it is the responsibility of the Investigator to review all documentation (e.g. hospital progress notes, laboratory, and diagnostic reports) relative to the event. The Investigator will then record all relevant information regarding an AE/SAE in the eCRF. All details of any treatments initiated due to the AE should also be recorded in the subjects' notes and the eCRF.

All AEs will be documented in the appropriate section of the eCRF. Among these AEs, all SAEs (refer to [Section 6.10.1.2](#)) will be additionally documented in an SAE Report. The following will be recorded for each event on the eCRF:

- A description of the AE in medical terms, not as reported by the subject. Whenever possible, a diagnosis should be given when signs and symptoms are due to common etiology (e.g., cough, runny nose, sneezing, sore throat, and head congestion should be reported as “upper respiratory infection”).
- The date of onset (start date).
- The date of resolution (stop date).
- The severity as assessed by the investigator according to the definitions in [Section 6.10.4](#).
- The causal relationship to study drug as assessed by the investigator; the decisive factor in the documentation is the temporal relation between the AE and the study drug (refer to [Section 6.10.5](#)).

- Action taken for study drug (none, study drug discontinued, study drug dose reduction, study drug delayed).
- Other action(s) taken (none, concomitant medication given, new or prolonged hospitalization, procedural surgery).
- The outcome according to the following definitions:
  - Recovered with sequelae;
  - Recovered without sequelae;
  - Ongoing, no therapy;
  - Ongoing, therapy;
  - Died, or
  - Change in toxicity grade/severity.
- Serious Adverse Event (as defined in [Section 6.10.1.2](#)): yes or no.

If, in any subject, the same AE occurs on several occasions (unless the AE is continuous and of stable grade), then the AE in question will be documented and assessed each time. For an SAE, the information listed above to be recorded in the eCRF will also be recorded in the SAE Report. Only AEs that fulfill the criteria for SAEs (refer to [Section 6.10.1.2](#)) should be recorded in the SAE Report.

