#### 6.10.6. Reporting Adverse Events

Each AE is to be classified by the investigator as serious or non-serious. This classification determines the reporting procedures to be followed ([Table 1](#)).

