**Table 1 Reporting Requirements for Adverse Events**

| Gravity | Reporting Time         | Type of Report |
|----------------|-------------------------------|-----------------------|
| Serious        | Within 24 hours               | Complete AE eCRF      |
| Non-serious    | Per eCRF submission procedure | Appropriate AE eCRF   |

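### The SAE definition in Protocol 6.10.1.2 is internally inconsistent: its outcome list omits a first hospital admission, which the paragraph below it treats as already serious

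*Protocol*

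**What the plan says.** Protocol 6.10.1.2 defines an SAE as "any AE occurring at any dose that results in any of the following outcomes" and then gives five outcomes: death, a life-threatening event, a hospitalization item, disability or incapacity, and congenital anomaly. The hospitalization item reads in full "Prolongation of existing hospitalization or re-hospitalization".

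The next paragraph of the same section brings in important medical events: "Important medical events that may not result in death, be life threatening, or require hospitalization may be considered an SAE when" medical judgment finds that the subject may be in jeopardy and may need intervention to prevent a listed outcome. One of its examples is "blood dyscrasias or convulsions that do not result in inpatient hospitalization".

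Several later sections depend on this definition:

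- Protocol 6.10.3 limits the SAE Report: "Only AEs that fulfill the criteria for SAEs" belong in it. The same section lists "new or prolonged hospitalization" among the other actions taken for any adverse event, with seriousness as a separate yes/no item.
- Protocol 6.10.6 has the investigator classify each event as serious or non-serious and says: "This classification determines the reporting procedures to be followed". Table 1 sets the time for serious events at "Within 24 hours"; non-serious events follow the ordinary eCRF submission procedure.
- SAP 4.6.1 tabulates and lists serious TEAEs. The SAP has no definition of serious of its own.

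**The concern.** The list and the paragraph beneath it give different answers for one kind of event: an adverse event that puts a subject who is not already an inpatient into hospital for the first time. The list does not name it. The paragraph is written as though the list did.

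What is at stake is consistent safety reporting for a new inhaled agent. The section 6.10.1.2 criteria decide whether an event gets an SAE Report, whether it is reported within 24 hours, and whether it is counted in the serious-TEAE table. They also feed the expedited reporting of serious unexpected reactions (Protocol 6.10.1.4), notification of the IRB (6.10.7 and 9.1), and sponsor review of SAE reports (9.5). If the criteria can be read in two ways, two sites may classify the same event differently, and the table would then mix two definitions.

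**Working it through.** No arithmetic applies. The check sets the texts side by side and follows one event through them.

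**Step 1. What each text says about a first admission**

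| Place | Wording | Effect for a first admission |
|---|---|---|
| Protocol 6.10.1.2, outcome list | "Prolongation of existing hospitalization or re-hospitalization" | Not covered; both halves need an earlier admission |
| Protocol 6.10.1.2, next paragraph | "Important medical events that may not result in death, be life threatening, or require hospitalization may be considered an SAE when" | Groups needing hospitalization with death and threat to life, as if already listed |
| Protocol 6.10.1.2, example | "blood dyscrasias or convulsions that do not result in inpatient hospitalization" | The contrast makes sense only if admission would settle the matter |
| Protocol 6.10.3, other actions taken | "new or prolonged hospitalization" | Records the admission but is not a seriousness criterion |
| Protocol 6.10.1, what an AE does not include | Elective-surgery, social and convenience admissions | Removes admissions with no untoward event; does not reach an admission caused by an AE |
| SAP 4.6.1 | Serious TEAEs are counted | Takes over the protocol's classification |

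The first row conflicts with the second and third. No row adds the missing criterion.

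**Step 2. Can such an event arise?** Protocol section 6 allows assessments and treatments in a hospital or a doctor's office, and section 3.1 has follow-up by telephone on the day after imaging (+3 days). At least some subjects are therefore not inpatients while events are being collected. That is an inference; the documents do not describe subjects as outpatients.

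**Step 3. Follow one event on the literal list.** Suppose a subject at home has an adverse event and is admitted for the first time. The event is not fatal, life-threatening or disabling.

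1. No listed outcome is met.
2. The important-medical-event clause may apply, but it is permissive, turns on judgment, and refers back to preventing one of the listed outcomes.
3. If the investigator applies it, the event is serious and everything downstream works.
4. If not, the event is non-serious: no SAE Report (6.10.3), the ordinary eCRF timeline (6.10.6 and Table 1), and no entry in the serious-TEAE table (SAP 4.6.1).
5. In either case it is an adverse event and appears in the general TEAE tables (SAP 4.6.1).

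**Step 4. Follow the same event on the paragraph.** A site that takes the paragraph's premise at face value calls the event serious because the subject was admitted, with no further judgment.

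Steps 3 and 4 can end in different classifications of the same facts, and nothing in the documents says which text governs.

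**The case against.** The strongest reply is that section 6.10.1.2 should be read as a whole. The paragraph counts convulsions that did not lead to admission, and bronchospasm treated in an emergency room or at home, as candidates for serious. An admitted case is then serious all the more. An admission to avert death, a threat to life or disability also fits the important-medical-event clause without any hospitalization bullet. There are safeguards too. Section 6.10.7 encourages discussion with Pharmacovigilance when reportability is unclear. Section 9.5 has the sponsor's physician monitor safety data throughout. Section 7 provides for eCRF review and edit checks. The admission is recorded in the same form as the seriousness flag, so a mismatch can be seen.

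Much of this stands. It narrows the gap to admissions without those risks and to cases where discretion is not used. It does not close the gap: the clause is permissive, the discussion is encouraged but not required, and no check of the flag against the action field is specified.

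A reader might infer more than the documents support:

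- **That such events escape reporting.** This follows only from applying the list literally and not using the clause. The supportable statement is that classification is left to judgment.
- **That a first admission is the most likely serious outcome of a reaction.** Nothing supports this. Section 1.5 reports 103 people exposed with no TEAEs, and section 1.3 describes a more than 1000-fold fall in xenon concentration before 40 breaths, reached in 2-3 minutes.
- **That the action field in section 6.10.3 contradicts the list.** It does not. It applies to any adverse event, and seriousness is a separate item. The inconsistency lies within section 6.10.1.2.
- **That one missed event shifts the serious-event rate by 1/32.** The event is hypothetical, and 32 is the completer target. The Safety Analysis Set is everyone given at least one dose of either gas, and discontinued subjects are replaced, so its size is not fixed at 32.
- **That the sponsor chose to exclude new admissions.** Nothing says so, and the paragraph points the other way. The section attributes its definition to federal regulation, but that text is not in the documents, and this point does not rest on it.

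**Conclusion.** The point holds as an internal inconsistency in Protocol 6.10.1.2 that should be corrected. The list omits a first inpatient admission, the paragraph below presupposes it, and neither document supplies it elsewhere. The conclusion needs only those texts and the modest assumption that some subjects are not inpatients while events are collected.

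Its reach is limited. It concerns adverse events whose only claim to seriousness is a first admission and for which the important-medical-event clause is not applied. The number of such events cannot be estimated from the documents and may be zero. The primary and secondary efficacy analyses, the analysis sets and the equivalence conclusion are unaffected. What is affected is whether the SAE Report, the 24-hour timeline and the serious-TEAE table rest on one definition at every site.

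**What to change.** Reconcile the bullet with the paragraph that follows it. One suitable wording is: *inpatient hospitalization (initial or repeat), or prolongation of a stay already under way*. Keep the section 6.10.1 exclusions for elective-surgery, social and convenience admissions, so that planned resection surgery does not become an SAE by itself. If the SAE form or eCRF guidance repeats the list, change it there too; those forms are not in the documents.

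Before database lock, take every adverse event with "new or prolonged hospitalization" recorded as an action taken and check its seriousness flag against the reconciled definition, querying the site where the two disagree. The serious-TEAE table in SAP 4.6.1 then needs no change of its own.

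The cost is a one-line protocol correction, a short data check, and possibly a few more SAE reports. It alters a reporting definition and no aspect of how subjects are treated.
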